#### Blinding and Randomization

Patients will be randomly assigned to one of the 2 treatment groups in equal ratio, Randomization will be done centrally using a randomized block design, with blocks of 4 using the Pqantadosi Randomization software There will be a randomization table provided to the person dispensing the devices. The unblinded, lead research coordinator will keep the data in a secure database and will not be involved in any of the patient recruitment or study procedures. All other research coordinators, investigators, and nurses involved will be blinded to group allocation. In general, the study biostatisticians and the person dispensing will be the only people un-blinded throughout the duration of the study.

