#### **DESIGN AND METHODS**

The study will recruit a total of 50 subjects and will take place in a well-established outpatient treatment center (Brightview). Brightview is a private addiction treatment center located in Cincinnati, Ohio. The site PI at Brightview will be [name] [name] (MD, ABIM, ABAM DABPM), a board-certified physician in addiction medicine. [name] (PhD) will be a Co-investigator. The volume of patients treated for opioid use disorder (OUD) at this facility is sufficient for patient recruitment in this study. [name] will be responsible for patient recruitment and overseeing the entire project at Brightview. He will monitor the health of all patients in the study per standard clinical practice. [name] will be responsible for patient recruitment as well and monitor protocol adherence as well as supervise data collection, entry, and analysis.

This study will involve a double-blind, randomized, controlled trial with active BRIDGE or sham device (Figure 3). The sham device will be identical in appearance to the active device but will have no electrical current. Both providers and patients will be blinded to treatment allocation throughout the study. Participants will be 18 years or older who speak English and meet criteria for opioid use disorder based on the Diagnostic and Statistical Manual of Mental Disorders-5. Patients going through acute opioid withdrawal will be assessed for the severity of opioid withdrawal using the Clinical Opioid Withdrawal Scale (COWS). Additional demographic data will be collected at presentation including age, sex, duration of opioid misuse, types of medications or illicit drugs used as well as the presence of other medical conditions. After the severity of opioid withdrawal is established (COWS score  $\geq 10$ ), subjects will be randomized in blinded fashion. Once the patient is consented, a visual analog scale (VAS) for pain and an opioid craving scale (OCS) will be completed. Baseline cognitive function will be measured with the Stroop test using the CNS Vital Signs (CNSVS) in-office neurocognitive testing software https://www.cnsvs.com/index.html. This instrument measures executive function. The test takes approximately

4 minutes to administer and will be performed at the same intervals as COWS score, pain and craving assessments before and after device placement.

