#### DATA MANAGEMENT

Subjects will be randomized in a 1:1 ratio to receive either active or a sham device. Randomization in blocks of 10 (5 for each treatment) will be determined using the computer program randomization.

The severity of opioid withdrawal signs and symptoms will be assessed with the COWS at several time points: 1) pre-device placement, 2) 1-hour post placement of sham or active device, 3) two hours post placement (approximately one hour after first dose of buprenorphine), 4) at subsequent follow-up in clinic on day 2 and 5) at final follow-up in clinic on day 5 prior to removal of device. The visual analogue pain and craving scale will also be administered at intervals to monitor patient comfort: 1) pre-device placement, 2) 1-hour post placement of sham or active device, 3) two hours post placement (approximately one hour after first dose of buprenorphine),4) at subsequent follow-up in clinic on day 2, 5) in clinic or remotely (via phone) on days 3 and 4, and 6) at final follow-up in clinic on day 5 prior to removal of device. Assessment of cognitive function (CNSVS) will be recorded at 1) pre-device placement, 2) 1-hour post placement of sham or active device, and 5) at final follow-up in clinic on day 5 prior to removal of device. One hour following placement of either sham or active device, the patients will be given the first dose of buprenorphine with a starting dose of 2, 4 or 8 mg at the blinded provider's discretion based on BMI, patient previous experience with BUP, patient apprehension or other factors. Adjustments to this dose will not be made for at least an hour after receiving the first dose but the providing clinician may order additional buprenorphine after one hour as indicated by initial response, previous experience, presence of precipitated clinical opioid withdrawal scale (COWS) and BMI. Subsequent adjustments will be made based on the blinded provider's discretion and patient needs and comfort as per clinic standard. Ancillary (supportive) medications to help manage signs and symptoms of opioid withdrawal will NOT be allowed for one hour after the first dose of buprenorphine. Following the first hour, symptom control medications including ibuprofen, clonidine, ondansetron, loperamide, and acetaminophen may be furnished or prescribed. A medication log will be provided to track usage of this modality. Subjects will remain blinded and keep the device on for 5 days regardless of randomization status. Subjects will be asked to return to clinic for additional induction visits based on the clinic standard of care which will be Day 2 and in some cases Days 3 & 4. In order to monitor whether neurostimulation with the BRIDGE has any added benefit for patients on outpatient opioid agonist therapy, subjects (regardless of active or placebo) will be reassessed using OCS and VAS at each subsequent visit, or remotely (via phone) when unrequired to return to clinic, during the 5-day trial.

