#### Subject recruitment and enrollment

Subjects presenting to the outpatient clinic at Brightview health will be identified by the attending physician and the patient will be approached for inclusion in the study by the research coordinator if they meet criteria. The principal investigator, a co-investigator or research coordinator will introduce the study to the patient during the initial clinic visit and will explain the details and purpose of the study during an informed consent discussion and obtain consent. Once the patient had enough time to consider participation, understand the risks and benefits and agree to participate, he/she will sign informed consent and HIPAA documents.

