#### NSS-2 BRIDGE placement details:

- 1. A research coordinator will document the patient ID, name and the device serial number in the study database.
- 2. The research coordinator or provider will record baseline answers to questionnaires and will also record vital signs (temperature, heart rate and blood pressure).
- 3. The neurostimulator placement will be performed as directed and per BRIDGE training protocol instructions identical to prior IRB approved protocols.

- 4. Before device placement, the subject caretakers should be advised that some discomfort is normal at first. If the discomfort persists or worsens after a few minutes the medical provider will be notified. The patients will be advised that they may feel a slight pulsing sensation and perhaps a warming sensation in the ear to which the electrodes are affixed. The pulsing and warming sensation may disappear after approximately 5 minutes. If the discomfort level increases the offending array can be repositioned until the patient's discomfort level decreases to an acceptable level.
- 5. Subjects will be advised not to immerse the device in water as the device is water resistant but not water proof. If showering or washing their hair, placing a dry wash cloth over the area to help protect the device will be recommended. Subjects will be given a contact person (Principal investigator, Co-investigator or Research coordinator) to call if they are having any problems with the device or if it falls off.
- 6. The device may be removed by the patient or a caretaker if at home. If uncomfortable doing so or unable to carry out the instructions, an outpatient appointment will be made and the device will be removed by the investigators.
- 7. If removed at home, the patient will be asked to return the used device for proper disposal when they return the following week.

#### Figure 5

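### Each stated block size is fixed and printed in the protocol; varying and withholding it is a cheap precaution in case the blind leaks

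*Combined protocol and SAP*

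**What the plan says.** Two sections describe the randomization. Blinding and Randomization: "Randomization will be done centrally using a randomized block design, with blocks of 4". The first Data Management section: "Subjects will be randomized in a 1:1 ratio to receive either active or a sham device", followed by "Randomization in blocks of 10 (5 for each treatment) will be determined using the computer program randomization". Neither says that sizes vary or are kept from recruiting staff, and no separate restricted randomization document is mentioned.

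The trial has one running sequence: "The study will recruit a total of 50 subjects and will take place in a well-established outpatient treatment center", and no stratification is stated. On recruitment, the plan says "Subjects presenting to the outpatient clinic at Brightview health will be identified by the attending physician" and "The principal investigator, a co-investigator or research coordinator will introduce the study to the patient during the initial clinic visit".

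Blinding and Randomization also sets out safeguards. Randomization is central. The table goes to the person dispensing devices. The unblinded lead coordinator takes no part in recruitment or procedures, and all other coordinators, investigators and nurses are blinded.

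On the blind itself, Design and Methods says "The sham device will be identical in appearance to the active device but will have no electrical current", and item 4 of the placement details says "The patients will be advised that they may feel a slight pulsing sensation".

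**The concern.** Concealing the list does not by itself make allocations unpredictable. In a permuted block of known length, anyone who forms an impression of what earlier patients received can work out which arm is more likely next, and sometimes which arm is certain.

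The plan leaves routes to such impressions. The sham carries no current, while patients are told to expect pulsing or warming. A large effect is expected within the hour (the power section cites a difference above 12 points in the earlier study). Entry depends on a COWS of at least 10, which the Safety Monitoring Plan has nursing staff or the provider score, and on whom staff approach. If allocations could be partly forecast, expectation could influence who is enrolled and when. Neither the intention-to-treat population nor the t-test removes that kind of bias.

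**Working it through.** **Inputs.** Block size 4 (Blinding and Randomization) or 10 (Data Management); 1:1; 50 patients, one sequence; SD about 6, 25 per arm, two-sided alpha 0.049 (power section). Two inputs are assumptions, because the documents give no figure: the accuracy q with which staff sense each earlier allocation, and the 1-point selection preference.

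**The plan's own figure.** Power for 0.94 SD with 25 per arm at alpha 0.049 is 0.901 (noncentral t, 48 df). This reproduces the stated 90%, and the present point does not affect it.

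**Perfect sensing.** The guesser picks the arm used less so far in the block. For a block of 4, the chance of a correct guess is:
- first patient: 1/2
- second: 2/3
- third: (2/3)(1/2) + (1/3)(1) = 2/3
- fourth: 1

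The sum is 2.83 of 4, or 70.8%. Over 50 patients there are 12 full blocks and a part-block of two: (12 × 2.833 + 1/2 + 2/3)/50 = 70.3%. Fully determined allocations number 1 + 1/3 = 1.33 of 4 (33%). The same enumeration for a block of 10 gives 6.53 correct (65.3%) and 1.67 determined (17%).

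**Imperfect sensing.** Simulation of 20,000 trials of 50 patients, block boundaries known. The last column is undisclosed, randomly mixed blocks of 4 and 6, guessed from the running imbalance.

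| Assumed q | Known 4 | Known 10 | Undisclosed 4/6 |
|---|---|---|---|
| 50% (blind intact) | 50% | 50% | 50% |
| 60% | 53.0% | 51.7% | 51.0% |
| 80% | 59.8% | 56.0% | 53.7% |
| 100% | 70.3% | 65.3% | 69.0% |

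**Sensitivity of the last column.** A guesser who does not know the sizes can instead bet against the last allocation sensed. Consecutive patients differ with probability 2/3 within a block of 4, 3/5 within a block of 6 and 1/2 across a boundary. With equal numbers of each block size the average is (3 × 2/3 + 1/2 + 5 × 3/5 + 1/2)/10 = 0.60. At q = 80% the chance of a correct guess is 0.5 + (0.60 − 0.5)(2 × 0.8 − 1) = 56%. So the benefit over known blocks of 4 survives this rule (60% to 56%), but the benefit over known blocks of 10 does not.

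**Bias.** Suppose staff enrol a patient expected to do 1 point better when they guess active and 1 point worse when they guess sham. With a proportion p of guesses correct, each arm mean shifts by (2p − 1) in opposite directions, so bias = 2(2p − 1) × 1 point.
- Blocks of 4, q = 80%: 2(2 × 0.598 − 1) = 0.39, about 0.4 points, or 0.4/6 = 0.07 SD and 0.4/5.7 = 7% of the detectable difference.
- Blocks of 10, q = 80%: 2(2 × 0.560 − 1) = 0.24 points.
- Blocks of 4, q = 100%: 2(2 × 0.703 − 1) = 0.81, about 0.8 points.

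**Effect on the final test with no true effect.** The two-sided error moves from 4.9% to 5.1% (0.24 points) or 5.5% (0.4 points). The chance of falsely favouring the device rises from about 2.5% to about 4% (0.4 points) or 7% (0.8 points).

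**The case against.** The best defence is that the mechanism needs several things to go wrong together, and the plan guards against the first of them. With the blind intact, the block size gives no advantage at all. The sham looks identical, both arms receive the same advice about sensation, and the advice says the sensation may fade after about five minutes. In the sham-controlled adolescent trial cited under adverse events, ear discomfort was three against three. That does not show that the blind holds here, but it gives no support to a high sensing accuracy.

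A reader might also infer that one small team identifies patients, scores COWS, fits the device, hears about sensations and knows the block size. The documents do not say so. The attending physician identifies patients, a coordinator or investigator approaches them, an MD or APN fits the device, and nurses or the provider score COWS. No collection of sensation reports is described. That recruiters read the randomization sections is an inference from their roles, and the two conflicting sizes would leave them unsure which applies.

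The remedy is limited too. Under perfect sensing, mixed 4/6 blocks give 69%, barely better than blocks of 4 and worse than blocks of 10. If allocations were sensed that well, biased scoring of COWS would matter more than block size.

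All of this stands, and it sets the size of the point. It does not change the fact that each stated size is fixed and disclosed, or that protecting the list cannot stop inference from patients already seen.

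**Conclusion.** The point holds as a modest, conditional weakness in the design. Under either stated size, partial prediction follows if the blind leaks: about 53%, 60% or 70% correct with blocks of 4, and 52%, 56% or 65% with blocks of 10, at assumed accuracies of 60%, 80% or 100%. Adding the assumed 1-point preference, the bias at 80% is about 0.4 or 0.24 COWS points, against a target of 5.7. It is zero if the blind holds.

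The stronger reading, that recruiting staff can predict allocations and that selection bias should be expected, is not supported. The documents give no evidence on sensing accuracy and none that staff track block position. The case for acting is that the change costs almost nothing while the two sections are being reconciled anyway.

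**What to change.** When the two sections are reconciled, generate the list with block sizes varied at random (for example 4 and 6). Hold the sizes only in the statistician's restricted randomization file, and state in both places only '1:1, permuted blocks of varying size'. Reporting the end-of-treatment device guess by arm, which is already collected from patients, would show how well the patient blind held.

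Cost: one regenerated list and two edited sentences. The final split may miss 25:25. With 4/6 blocks and 50 patients, the last incomplete block contributes two or four patients, so the worst split is 26:24. Fixed blocks of 4 already produce that with probability 1/3, since 50 = 12 × 4 + 2 and the last two patients fall in the same arm one time in three. The loss of power is negligible, but device supply should be checked, because the guaranteed minimum is 25 of each type.

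If the list is already in use, leave it alone and at least remove the block sizes from staff-facing text.

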#### Unblinding

Unblinding (or unmasking) patient's treatment assignment is only done when knowledge of the blinded treatment is necessary, for the treatment of an adverse event. Where possible patient will remain on trial and where medically feasible on assigned treatment. For all unblinding if possible, any assessors of subsequent outcomes will remain blinded. Record will be kept on unblinding and patients will be excluded from per protocol analysis but not the intent to treat analysis.

#### DATA MANAGEMENT

Subjects will be randomized in a 1:1 ratio to receive either active or a sham device. Randomization in blocks of 10 (5 for each treatment) will be determined using the computer program randomization.

The severity of opioid withdrawal signs and symptoms will be assessed with the COWS at several time points: 1) pre-device placement, 2) 1-hour post placement of sham or active device, 3) two hours post placement (approximately one hour after first dose of buprenorphine), 4) at subsequent follow-up in clinic on day 2 and 5) at final follow-up in clinic on day 5 prior to removal of device. The visual analogue pain and craving scale will also be administered at intervals to monitor patient comfort: 1) pre-device placement, 2) 1-hour post placement of sham or active device, 3) two hours post placement (approximately one hour after first dose of buprenorphine),4) at subsequent follow-up in clinic on day 2, 5) in clinic or remotely (via phone) on days 3 and 4, and 6) at final follow-up in clinic on day 5 prior to removal of device. Assessment of cognitive function (CNSVS) will be recorded at 1) pre-device placement, 2) 1-hour post placement of sham or active device, and 5) at final follow-up in clinic on day 5 prior to removal of device. One hour following placement of either sham or active device, the patients will be given the first dose of buprenorphine with a starting dose of 2, 4 or 8 mg at the blinded provider's discretion based on BMI, patient previous experience with BUP, patient apprehension or other factors. Adjustments to this dose will not be made for at least an hour after receiving the first dose but the providing clinician may order additional buprenorphine after one hour as indicated by initial response, previous experience, presence of precipitated clinical opioid withdrawal scale (COWS) and BMI. Subsequent adjustments will be made based on the blinded provider's discretion and patient needs and comfort as per clinic standard. Ancillary (supportive) medications to help manage signs and symptoms of opioid withdrawal will NOT be allowed for one hour after the first dose of buprenorphine. Following the first hour, symptom control medications including ibuprofen, clonidine, ondansetron, loperamide, and acetaminophen may be furnished or prescribed. A medication log will be provided to track usage of this modality. Subjects will remain blinded and keep the device on for 5 days regardless of randomization status. Subjects will be asked to return to clinic for additional induction visits based on the clinic standard of care which will be Day 2 and in some cases Days 3 & 4. In order to monitor whether neurostimulation with the BRIDGE has any added benefit for patients on outpatient opioid agonist therapy, subjects (regardless of active or placebo) will be reassessed using OCS and VAS at each subsequent visit, or remotely (via phone) when unrequired to return to clinic, during the 5-day trial.

Overall, the study will have very little deviation from the current standard of practice to treat substance use disorder (SUD), with the exception of the first hour of medical management which will be effected without

buprenorphine or symptom control medications, and the second hour during which symptom control medications will not be used. Current standard of practice in the clinical setting is to give the first dose of buprenorphine on Day 1 after initial screening, followed by a second or third dose prior to discharge home. Patients will be sent home and monitored as outpatients and asked to return to clinic within 2-5 days. The current study will not deviate from clinical practice after Day 1 with the exception of having either the BRIDGE device or sham device for 5 days. The device will be removed at the clinic visit on Day 5 and disposed of in a sharps container. If the patient cannot come back on day 5, they will be instructed to remove the device at home and bring it back at the next clinic appointment for proper disposal.

#### Figure 3

If at any time the patient wishes to discontinue the BRIDGE device and receive standard treatment for opioid withdrawal outside the study, he/she will be allowed to do so.

The study will involve the use of the NSS-2 BRIDGE device, an ambulatory, neurological device which consists of a battery powered, externally affixed generator with 4 wire leads: 1 double needle electrode lead and 3 single point electrode needle leads (Figure 4). The device delivers low voltage (3.2V) stimulation in alternating frequencies for a total of 5 days (around the clock). The arrays are designed to produce a field effect. The leads will be placed percutaneously in the external ear with the help of a transilluminator to visualize the neurovascular bundles. Three electrodes will be placed on the ventral aspect and one on the dorsal aspect of the ear. The electrodes will be taped and secured behind the ear next to the generator itself which is secured to the skin with adhesive. The placement of the devices is within standard of care by properly trained medical providers or physician extenders.

Participants in this study will be males and females between the ages of 18 and 60 years who are English speaking and capable of giving informed consent. Applicants must fulfill the criteria for opioid use disorder based upon the Structured Clinical Interview for DSM-5 (SCID). In addition, they must have an opioid (morphine, 6MAM, oxycodone or metabolites, hydrocodone or metabolites or fentanyl or metabolites, methadone or metabolites) positive urine immunoassay test during the screening process and have evidence of opioid withdrawal with COWS score  $\geq 10$ . They must be healthy, with no significant medical illnesses (e.g., insulin dependent diabetes), and without significant psychiatric illness (e.g., schizophrenia) other than their drug dependence.

